All potential risks of modafinil will be outlined in the informed consent document and discussed with the patient prior to enrollment. Patients will also be advised that there may be unforeseen risks not outlined in the ICF. Based on the package insert, eligibility criteria will exclude pregnant women, and a urine pregnancy test will be required prior to study enrollment. Women of childbearing age will be advised of the risk of decreased effectiveness of hormonal contraception with modafinil use and be advised to use a form of birth control that does not involve hormonal contraception (spermicide or condoms) during the study and for one month after discontinuation of modafinil treatment. Participants with a history of hepatic impairment, participants over age 65, and participants who use warfarin, phenytoin, MAOIs and cyclosporine will be given dose limitations that will not exceed half of the maximal daily dose for healthy patients (50-100 mg once-twice daily as tolerated). Patients will be advised to monitor for common side effects of modafinil including headache, nausea, nervousness, rhinitis, diarrhea, back pain, anxiety, insomnia, dizziness, and dyspepsia while on modafinil, and if these symptoms occur or worsen, to alert the study team, during which time dose reduction or discontinuation will be discussed. Participants who experience worsening depressive symptoms, psychosis, increased suicidality, or suspected allergic reactions (rash, hives, mouth sores, blisters, swelling of the face, eyes, lips, tongue, or throat, trouble swallowing or breathing, fever, shortness of breath, swelling of the legs, yellowing of the skin or whites of the eyes, or dark urine) will be instructed to stop treatment immediately and contact the study team. Participants are also advised not to consume alcohol per the drug label. Participants should be instructed to call study team when new drugs are added or removed from their drug regimens so that drug interactions can be assessed. Participants may choose to discontinue their treatment at any time if they experience any untoward effects that they believe are related to modafinil, but will be encouraged to remain in the study until completion for monitoring. Adverse events and severe adverse events will be assessed/reported regularly and on an as-needed basis in accordance with the protocol, GCP, and IRB standards (see sections 7.5 and 8). Action involving possible PI discontinuation of study drug will be determined promptly in accordance with the protocol, GCP and IRB guidelines, as well as the medical monitor (see section 10 and 13).

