4.2 Exclusion Criteria

1. Current shift work sleep disorder, or narcolepsy diagnosed with polysomnography and multiple sleep latency test (diagnoses in which modafinil is already widely accepted as symptomatic care)
2. History of MS relapse within the last 30 days prior to screening (participants will be considered eligible after the 30-day window);
3. Current stimulant or wake-promoting agent use such as amantadine (Symmetrel), modafinil (Provigil), short or long acting methylphenidate (Ritalin/Concerta), dextroamphetamine (Dexedrine), dextroamphetamine-amphetamine (Adderall, Adderall XR), lisodexamfetamine (Vyvanse), armodafinil (Nuvigil), or amphetamine (Adzenys XR-ODT, Dyanavel XR, and Evekeo) within 30 days of screening (if present, patients could still be eligible after a 30-day washout);
4. For female participants only: Pregnancy or breastfeeding (modafinil is contraindicated in these conditions);
5. For female participants only: Reliance on hormonal contraception (such as birth control pills, shots, implants, patches, vaginal rings) AND concomitant unwillingness to use alternative non-hormonal means of birth control (spermicide or condoms) during the course of the study (modafinil can decrease the effectiveness of oral contraception);
6. Current suicidal ideation (SI) with intent or plan (per a response of ≥ 1 on the suicide item from the Patient Health Questionnaire-9); these individuals will be assessed by a study psychologist and referred for urgent mental health treatment† (people with SI but no intent or plan will be included).
7. Known hypersensitivity to modafinil or armodafinil or its inactive ingredients.
8. History of the following cardiovascular conditions: recent myocardial infarction (last 6 months prior to screening), unstable angina, left ventricular hypertrophy, mitral valve prolapse, NYHA class III or IV congestive heart failure
9. Diagnosis of hypertension within the past year not managed by a health care provider
10. Recent history (within 1 year) of prescription or illicit stimulant abuse (such as cocaine, amphetamine, methamphetamine)
11. Any other medical, neurological, or psychiatric condition that, in the opinion of the investigators, could affect participant safety or eligibility.

†Participant behavior or comments that suggest imminent threat will prompt immediate 911 activation. Behavior or comments that suggest SI with plan but no immediate threat will prompt psychiatric ER referral

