6.1 Screening/Baseline Visit

Depending on state or institutional COVID-19 restrictions at time of screening, baseline visits may be conducted virtually (via video meeting) or in-person. Even when in-person visits are permitted, participants will still be given the option for virtual visits.

For in-person visits, subjects will be seen at one of several UM or UW sites for baseline visit activities, including but not limited to the University of Michigan Taubman Neurology Clinic, Michigan Clinical Research Unit (MCRU), and the UW Medicine Multiple Sclerosis Center.

Informed consent will be obtained by qualified study staff. Inclusion and Exclusion Criteria will be reviewed. For virtual visits, the informed consent will be obtained digitally. See section 7.2.4.

The screening portion of this visit will include confirmation of eligibility via:

- 1) Participant self-report (e.g. FSS, PHQ-3, etc.)
- 2) Demographic information
- 3) Focused medical and surgical history as it relates to multiple sclerosis (subtype, prior disease modifying therapy use, disease duration), fatigue, mood disorders and hepatic issues (for modafinil)
- 4) Medication review

5) Neurologist assessment of eligibility

6) Pregnancy test (For individuals of childbearing age who identify their pregnancy status as unsure)

Eligible subjects will be randomized into one of the 3 study arms & will complete baseline assessments of self-reported fatigue, disability, sleep, exercise, self-efficacy, and other quality of life factors via online Redcap surveys.

6.2 Home monitoring 7-day PRO-Diary application (EMA) – BASELINE AND WEEK 12 ONLY: After completing the above screening/baseline activities, participants will receive instruction on use of the PRO-Diary® accelerometer watch, which the participant will wear during two separate 7-day “home monitoring” periods, at baseline (sent home with watch following baseline visit) and 12 weeks to assess physical activity (objectively measured via accelerometry), AND ecological momentary assessment (EMA) of fatigue intensity, fatigue impact, fatigability (ration of fatigue intensity/accelerometer activity counts), and sleep. See “Assessments” section.

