6.4 Interventions: see also section 5.3

Participants assigned to modafinil or combination therapy will be encouraged to pick up their first supply of modafinil within 7 days of the baseline visit. For virtual visits, participants will receive their first supply of modafinil by mail.

For those who receive CBT or combination therapy will also be able to schedule their first CBT session with the study team during or shortly after this baseline visit.

Participants will be instructed to start their assigned treatment following the 7-day home monitoring period. All treatments will be given for a total of 12 weeks, and treatments will begin after participants complete their first 7-days of PRO-Diary home monitoring.

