Additionally, protocol deviations will not be reported for missed EMA assessments administered by the PRO-Diary data during the home monitoring periods. We expect that there may be instances where participants are unable to complete the EMA questions (for example, if it alerts at a time that is inconvenient for them to answer or they forget to answer). Previous studies have shown that compliance with these repeated assessments is ~75%. The EMA assessments do not assess safety so a missed assessment is not a safety concern. We expect that participants will miss some of these assessments and have selected the length of the home monitoring periods (7 days) to make sure data validity is not compromised if participants miss some of the EMA assessments.

Any missed safety assessments will be reported as protocol deviations. Safety assessments are conducted by the coordinator in-person or by phone as applicable under the supervision of the study PIs during the baseline, 8 week, 12 week and 24 week study visits and during any other contact with the participant (e.g., phone calls).

1. Prescreening to Screening/Baseline Assessment Window: Study staff will aim to schedule the screening/baseline visit within 2 weeks of pre-screening. If the baseline visit is beyond 2 weeks from pre-screening, a study staff member will ask prior to the visit if there has been any change (in fatigue, meds, pregnancy, MS relapses, etc.) since pre-screening.
2. Baseline Home Monitoring Assessment Window: Participants will be given 14 days from their Baseline visit to complete their 7-day home monitoring period assessment. Although participants are asked to complete 7 days of home monitoring, a minimum of 3 full days of home monitoring data will be considered adequate (this allows for lost data due to technology malfunction/user error/illness/etc.).
3. Week 8 Assessment Window: A \pm 2-week (\pm 14 days) window around the Week 8 assessment will be considered allowable for data collection, as long as participants have not allowed modafinil treatment to lapse/run out during this time period.

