6.9 SCHEDULE OF ACTIVITIES

Study Activity	Baseline (week -1 to -2)	Weeks 1-7**	Week 8	Weeks 9-11	Week 12	Weeks 13-23	Week 24
Demographics	X						
Medical/Surgical History	X		X		X		X
Interview with a Neurologist for assessment of eligibility	X						
Krupp's Fatigue Severity Scale (FSS)	X						
Patient Health Questionnaire-3	X						
Medication review	X		X		X		X
Baseline urine Pregnancy test if applicable	X						
AE/SAE review (all participants)*	X		X		X		X
Randomization	X						
Modafinil dispensing (for Groups 2 and 3)	X		X				
Study Intervention Administration		X	X	X	X		
Treatment adherence			X		X		
Treatment Utilization Patterns (post-intervention)							X
Excess modafinil destruction (if applicable)					X		
Computer-based self-report measures							
Modified Fatigue Impact Scale (MFIS)	X		X		X		X
EDSS self-report	X						
STOP-BANG questionnaire	X						
RLS Index	X						

Epworth Sleepiness Scale	X		X		X		X
Insomnia Severity Index	X						
Sleep Hygiene Index	X		X		X		X
Patient Health Questionnaire-8	X		X		X		X
Generalized Anxiety Disorder-7	X		X		X		X
Brief Pain Inventory	X		X		X		X
Exercise (Godin)	X		X		X		X
PROMIS Self-Efficacy Scale	X		X		X		X
PROMIS Cognitive Function	X		X		X		X
MSQOL54- Quality of Life Subscale	X		X		X		X
NeuroQoL Ability to Participate in Social Roles & Activities	X		X		X		X
Post-Treatment Questionnaire					X		X
Patient Global Impression of Change					X		X
7-day home monitoring (PRO-Diary) measures							
Physical Fatigue Severity (4x/day)	X				X		
Mental Fatigue Severity (4x/day)	X				X		
Physical Fatigue Impact (4x/day)	X				X		
Mental Fatigue Impact (4x/day)	X				X		
Wake up time (1x/day)	X				X		
Bed time (1x/day)	X				X		
Sleep refreshed (1x/day)	X				X		
Rest breaks (1x/day)	X				X		
Cognitive clarity (1x/day)	X				X		
Cognitive speed (1x/day)	X				X		

Pain Severity (1x/day)	X				X		
Daytime physical activity (continuous)	X				X		

* For Modafinil-treated participants in Group 2 and 3, AE/SAE review will be additionally assessed at the following time intervals:

- 2-4 days after starting Modafinil
- 7-10 days after starting Modafinil

**Activities marked Week 1-7 begin after the baseline assessments, which include a 7-day home monitoring period.

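### Section 1.3 requires a urine pregnancy test before enrolment, but section 6.1 tests only participants who say they are unsure, so an unrecognised pregnancy can pass eligibility on self-report.

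*Combined protocol and SAP*

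**What the plan says.** Four places in the protocol bear on entry testing.

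- **Section 1.3 (Safety, Risks)**, in the account of how modafinil's risks are handled: pregnancy is an exclusion, and "a urine pregnancy test will be required prior to study enrollment". No group is named and no exception is made for women who report that they are not pregnant.
- **Section 4.2, exclusion 4** (female participants): "Pregnancy or breastfeeding (modafinil is contraindicated in these conditions"). No method of confirmation is given.
- **Section 6.1 (Screening/Baseline Visit)**, in the list of steps that confirm eligibility: "Pregnancy test (For individuals of childbearing age who identify their pregnancy status as unsure").
- **Section 6.9 (Schedule of Activities)**, marked at baseline only: "Baseline urine Pregnancy test if applicable". The condition is not defined.

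Two further provisions affect how the test would be done. Section 6.1 says of the baseline visit: "Even when in-person visits are permitted, participants will still be given the option for virtual visits". Section 6.4 adds: "For virtual visits, participants will receive their first supply of modafinil by mail".

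**The concern.** Sections 1.3 and 6.1 give different rules for who is tested. Section 1.3 presents the test as a requirement that supports the pregnancy exclusion. Section 6.1 makes it depend on the participant's own doubt. A woman who is pregnant but confident that she is not is the person a required test exists to find, and section 6.1 exempts her.

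The stake is participant safety. The protocol itself treats modafinil as contraindicated in pregnancy (section 4.2) and makes pregnancy a reason to stop it (section 13). There is also a conduct problem. Section 6.6 requires missed safety assessments to be reported as protocol deviations. If the pregnancy test counts as one, staff at the two sites cannot tell whether an untested woman is a deviation (section 1.3) or handled correctly (section 6.1).

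**Working it through.** No arithmetic tests this point. The check sets the rules side by side and asks whether anything else in the plan closes the gap.

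**Step 1: who is tested under each rule.** Read literally, section 1.3 would cover men, so some limit has to be supplied. The narrowest sensible one is participants who could be pregnant.

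| Participant | Section 1.3 (sensible reading) | Section 6.1 |
|---|---|---|
| Man, or woman past childbearing | Not tested | Not tested |
| Childbearing age, says unsure | Tested | Tested |
| Childbearing age, says not pregnant | Tested | Not tested |

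The rules differ in the third row only, and that row contains the unrecognised pregnancies.

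**Step 2: does the schedule decide?** No. The condition in section 6.9 could mean being of childbearing potential, which fits section 1.3, or being unsure, which fits section 6.1.

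**Step 3: is timing in conflict?** No. Section 6.1 places the test within confirmation of eligibility, which is consistent with a test before enrolment.

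**Step 4: does another safeguard detect an unknown pregnancy before modafinil is supplied?**

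- Exclusion 4 names no test, so for the third row it rests on self-report.
- Exclusion 5 removes only women who both rely on hormonal contraception and will not use a non-hormonal method. That exclusion and the contraception advice in section 1.3 concern preventing pregnancy, not detecting one.
- The section 6.6 re-check is a spoken question. When baseline falls more than 2 weeks after pre-screening, a staff member "will ask prior to the visit if there has been any change (in fatigue, meds, pregnancy, MS relapses, etc".). It can only bring out what the participant knows.
- The neurologist's eligibility assessment in section 6.1 has no further pregnancy test attached.
- The stopping rule in section 13 acts only once the pregnancy is known.

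None does.

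**Step 5: what happens after entry?** Of the 7 columns in section 6.9, the pregnancy test is marked in 1 (baseline, conditional) and modafinil dispensing in 2 (baseline and week 8). No scheduled test would therefore pick up a pregnancy missed at baseline. This count shows only that there is no later check. It does not measure the inconsistency, because section 1.3 promises only a test before enrolment.

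**Step 6: how many are affected?** Randomisation is 1:1:1 and two of the three arms receive modafinil, so an untested participant has a 2 in 3 chance of being assigned to it. The number of such participants cannot be derived. The protocol gives neither the expected sex and age mix nor the share of women of childbearing age who would call themselves unsure.

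**The case against.** The best defence is that section 1.3 is a risk narrative that names no population, that section 6.1 supplies the specific rule, and that the qualifier in section 6.9 signals a conditional test. On that reading there is a loose summary followed by a precise procedure, not a contradiction. This does not succeed, because it turns a stated requirement into a test triggered by the participant's own doubt. If the sponsor did intend self-report, section 1.3 overstates the protection and has to be corrected.

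It can also be said that nothing ranks section 6.1 above section 1.3, so staff who follow section 1.3 would test and no gap would arise. That is fair. The text shows that an untested pregnancy can pass, not that one will. But the list of screening steps is what a coordinator works from at the visit.

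Other points stand in part. The contraception advice, the neurologist's assessment and the stopping rule narrow the residual risk, although none detects an unknown pregnancy at entry. The arrangements for a remote urine test may be in the consent form, which section 12.2 treats as part of the protocol and which was not available for this review; that point is secondary. A baseline test also has limits: under section 6.6, treatment starts 7 to 14 days after the baseline visit, so even universal testing at that visit leaves an interval before the first dose.

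**Conclusion.** The concern holds. Sections 1.3 and 6.1 disagree about women of childbearing age who report that they are not pregnant, section 6.9 does not resolve it, and no other provision detects an unrecognised pregnancy before a drug the protocol calls contraindicated is supplied. The conclusion assumes that section 1.3 is meant for participants who could be pregnant, and that sites follow the section 6.1 list as written.

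The number affected is unknown. The issue concerns participant safety and eligibility only, with no bearing on sample size, power or the primary analysis. It should be corrected because the plan already promises the protection and the correction is cheap.

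**What to change.** Carry the section 1.3 commitment into the procedure:

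1. In section 6.1, replace the pregnancy test item with: *Urine pregnancy test for all participants of childbearing potential*, kept within confirmation of eligibility.
2. In section 6.9, replace the open condition with *all participants of childbearing potential*.
3. In section 1.3, name the same population so that the three sections match.
4. For virtual visits, state that a home urine test is mailed beforehand and its result is given to staff before randomisation. This still relies on the participant's report, but of a test result and not of a belief.

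The cost is wording changes in three sections, the small price of the kits, and possibly a short delay to virtual visits while a kit arrives.

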2. STUDY OBJECTIVES AND ENDPOINTS

2.1 Objectives

To compare the effectiveness of cognitive behavioral therapy, modafinil, and combination therapy on MS-related fatigue, in the context of common effect modifiers (depression, sleep disturbance, and disability level), using novel methodology that will capture the day-to-day experiences of patients with MS.

2.2 Endpoints

2.2.1 Primary Outcomes

Fatigue impact, as assessed by:

The mean difference in the Modified Fatigue Impact Scale (MFIS) score between 12 weeks and baseline (delta-MFIS), compared between the 3 treatment groups

2.2.2 Secondary Outcomes

Changes between 12 weeks and baseline in fatigue intensity, fatigue impact, and fatigability (measured using PRO-Diary ecological momentary assessment and accelerometry, measured 4x/day for 7 days, at baseline and 12 weeks), compared between the 3 treatment groups

2.2.3 Exploratory Endpoints

[figure not shown]
a) The mean difference in the Modified Fatigue Impact Scale (MFIS) score between 0 and 8 weeks, and 0 and 24 weeks (delta-MFIS), compared between the 3 treatment groups

b) clinical treatment patterns post-intervention

3. STUDY DESIGN

This is a randomized, rater blinded, comparative effectiveness trial. Consenting participants with MS and chronic problematic fatigue who meet all inclusion/exclusion criteria will be enrolled and randomized in a 1:1:1 ratio to receive telephone-based CBT (Group 1: 12 weeks of one-on-one telephone-delivered sessions of CBT that emphasize fatigue self-management skills; 8 weekly programmatic sessions + 2 maintenance/booster sessions), modafinil (Group 2: 100-200 mg once-twice daily as tolerated, for 12 weeks); or combination treatment with CBT (8 weekly sessions + 2 booster sessions) and 12 weeks of modafinil (Group 3).

Self-report measures of fatigue impact (Modified Fatigue Impact Scale - primary endpoint) and potential effect modifiers (depression, sleep, and MS subtype/disability level) will be assessed at baseline and at 8-weeks, 12-weeks and 24-weeks. Subjects will also undergo 1 week of continuous actigraphy monitoring and EMA data collection with a wrist-worn accelerometer pre-treatment (baseline) and 12 weeks (i.e., concluding at the end of therapy) to collect additional data on physical activity level, fatigue intensity (numerical self-report scale), and fatigability (ratio of EMA fatigue intensity/physical activity level). For specific measures and timeline see **Figure 1, study schematic, below.**

Online surveys

Primary Outcome: Fatigue Impact (*Modified Fatigue Impact Scale*)

Secondary outcome: Fatigue Severity (*Brief Fatigue Inventory*)

Effect Modifiers: Disability Severity (*self-report Expanded Disability Status Scale**)

Sleep disorders (*STOP-BANG*, insomnia severity index, Restless Legs Syndrome Index*, Sleep Hygiene Index*),

Depression (*Patient Health Questionnaire-9*)

Covariates: Demographics*, Anxiety (*Generalized Anxiety Disorder-7*), Pain (*Brief Pain Inventory*), Exercise (*Godin*)

Exploratory (12 weeks post-intervention) Outcomes: Fatigue impact/severity, clinical treatment utilization patterns at 24 weeks

7-day PRO Diary home monitoring

Ecological Momentary Assessment (EMA)

Secondary outcomes: Fatigue Impact (*self-report visual analogue scale*), Fatigue Severity (*self-report visual analogue scale*)

Effect Modifier: Morning assessment of sleep quality (*self-report visual analogue scale*)

Continuous actigraphy

Secondary outcome: Fatigability = ratio of EMA fatigue severity measure/physical activity level

Covariate: Daytime physical activity level

Drug dispense

*assessed at baseline visit only

†marks start of week 1

